BM cytology assessment (local) ¹⁰			x					x ¹⁴	x ¹⁵
Serum chemistry (local)	x		x		x		x	x	x
Automated CBC (local)	x	x	x	x	x	x	x	x	x
Cytogenetics (local)			x					x	

Part 2c – extension treatment phase, from cycle 5 (non-responders with stable or controlled disease who continue treatment at the investigator's discretion)

VISIT NO.	██████████
Study Day (± 3d)	████████████████████
Study Week	██████
Cycle	██████████
Concomitant MDS/AML specific medication	X
Pregnancy test	X
Imetelstat administration and drug account	X ¹⁶
Toxicity/AE assessment	X
LOCAL LABORATORY: Response assessment ¹⁷	X ¹⁸
CBC with differential (local)	X ¹⁸
PB blast assessment (local)	X ¹⁸
BM cytology assessment (local)	X ¹⁸

¹⁶ The dosing frequency for imetelstat (every ■ weeks or every ■ weeks) for these subjects will be determined at the discretion of the investigator.

17 Response assessment will be performed based on the combined response assessment criteria for MDS and AML based on IWG 2018 criteria (MDS) and the criteria of the European LeukemiaNet (AML). Additionally, the BM blast level at each response assessment will be the basis for deciding the frequency of treatment of imetelstat (every █ weeks or every █ weeks) until the next response assessment.

¹⁸ Optional response assessment and lab measurements to be done according to standard of care and/or only in case needed to assess and follow-up on (S)AEs and dose modifications

Part 3 – EOT and follow-up period (all patients)

VISIT NO.	██████ ██████ ██████	████ ██████ ██████	██████████ ██████ ██████████ ██████████	██████	██████████
Study Day (± 3d)	██████	██████	██████	██████████	██████████
Study Week	██████	██████	██████	██████	██████
Informed consent					
In- / exclusion criteria ³					
MDS/AML related medical history					
Concomitant MDS/AML specific medication	x	x	x	x	
Physical examination, vitals	x	x	x	x	
BMI	x	x	x	x	
Pregnancy test ⁴	x	x	x	x	
Toxicity/AE assessment	x	x	x	x	
Quality of life (QoL, EORTC QLQ-C30)	x	x	x		
Information on current state of condition / survival status	x	x	x	x	x
Central assessments / correlative analyses (EU: Leipzig, AUS: QIMRB, Brisbane)					
Bone marrow aspiration (5 mL sodium heparinized in separate tubes for central assessments)		x ²²			
Peripheral blood sampling for central assessments (10 mL sodium heparinized blood in separate tubes for central assessments)		x ²²			
Genetic profiling (NGS) at central laboratories		x			
MRD analyses at central laboratories					

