2.3.2 Secondary endpoints

The following secondary endpoints will be analyzed in this study.

Safety Measurements

- Toxicity as measured by NCI CTCAE v5.0

Efficacy Measurements

- Overall survival
 - defined as the time from the beginning of imetelstat treatment until death or censored at the date of the last follow-up visit.
- Progression-free-survival
 - defined as the duration of time from time of imetelstat treatment to time of progression or death, whichever occurs first. A subject who has neither progressed nor died will be censored on the date of last follow-up visit.
- Duration of best overall response
 - measured from the time measurement criteria are met for CR, CRi, PR or SD (whichever is first recorded, defined in Appendix III a)) until the first date at which recurrent or progressive disease is objectively documented.
- Best overall response
 - defined as the best response recorded from the start of the imetelstat treatment until disease progression (taking as reference for progressive disease the smallest measurements recorded since the treatment started).
- Response based on IWG 2023 criteria²⁴ (MDS population only)
 - assessed in [REDACTED] of treatment with imetelstat as:
 - Overall Response Rate (ORR) = CR (or CR equivalent)* + PR + CR_L + CR_h + HI, or
 - No response = Not meeting criteria for CR (or CR equivalent)*, PR, CR_L, CR_h, or HI.
 - For definition see Appendix III b).
- Scores of EORTC QLQ-C30 (version 3)
 - Global health status / QoL
 - Functional scales
 - Symptom scales / items

3 Translational program

Bone marrow and blood samples will be obtained at the indicated time points and stored for translational analyses, in particular assessment of response and measurable residual disease and identification of prognostic or predictive biomarkers. If adequate BM aspirate is not attainable, peripheral blood may be used if at least 5% or more BM blasts are present. If this is not the case, a BM biopsy will be required.

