The study will consist of a screening period, a primary treatment period (all patients), an extension treatment period (responders after 4 cycles of treatment only) and a posttreatment follow-up period. For the extension treatment period, in the absence of alternative treatment options, non-responders with stable or controlled disease may continue treatment at the investigator's discretion, in consultation with the sponsor, provided the disease remains controlled and none of the discontinuation criteria as described in section 7.7 are met.

[figure not shown]
Patients who stop the study treatment for any cause will undergo an EOT visit at the latest 14 days after the decision of treatment discontinuation. The EOT visit will be followed by a first follow-up visit (FU1) 28 ± 5 days after EOT and a second FU visit = EOS visit approximately 2 months after EOT. FU2/EOS can be carried out on the phone and represents the last study visit for the patient.

The End of Study is considered at the time the last patient completed their evaluation 6 months after the end of the primary treatment period (in case of a continued responder) or following their follow-up period (in case of a non-responder). For avoidance of doubt, for non-responders with stable or controlled disease who continue treatment at the investigator's discretion, the end of study will be defined as the end of the follow-up period for said patient or discontinuation from the trial, whichever occurs later. The sponsor will ensure that subjects benefiting from treatment with imetelstat will be able to continue treatment for as long as the subject's disease is controlled, provided that an adequate stock of imetelstat is available.

A summary of the study design is given in Figure 1.

For detailed description of study visits and procedures see VII Schedule of assessments and procedures and section 8.2.

Figure 1: Study flowchart

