#### 7.7.6 Progression-free-survival

Progression-free-survival (PFS) will be defined as the duration of time from time of treatment to time of progression or death, whichever occurs first. A subject who has neither progressed (defined as first time having Progressive disease (PD) or Progression or relapse after HI on response assessment) nor died will be censored on the date of the last observation. Therefore:

In case there was a progression or death:

PFS [days] = min(date of progression/death) – Drug administration date in Visit [REDACTED] +1

Otherwise, censoring date will be:

PFS [days] = date of last observation – Drug administration date in Visit [REDACTED] +1

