#### 7.7.7 Duration of response

Duration of response (DoR) will be measured from the time measurement criteria are met for CR, CRi, PR, MLFS or SD (whichever is first recorded, defined in section 11.2 Appendix 2 a)) until the first date at which recurrent or progressive disease is objectively documented for patients with confirmed CR, CRi, PR, MLFS or SD criteria met. Therefore:

DoR [days] = first date with PD response criteria after response – date of CR, CRi or PR response criteria +1

If there was no progressive disease documented, subject will be censored on last documented response assessment:

DoR [days] = date of last response assessment – date of CR, CRi or PR response criteria +1

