Due to the transient improvement seen in WBC and peripheral blasts in patients early in treatment, it was accorded to continue the study in an exploratory approach with a change in dose frequency. Therefore, binomial test will be performed with a two-sided 90% confidence interval for overall haematological response rate using the Clopper-Pearson method for both treatment cohorts (see 2.7) independently. Analysis will be repeated by subgroups (see 4.2). A SAS pseudo code can be:

```
proc freq data=Data;
  by Treatment_cohort;
  tables Hematological_response / binomial(all level="0") alpha=0.1 cl ;
  exact binomial /point;
run;
```

Response assessments of visit 5(W9 C3) and visit 9(W17 C5) will be listed.

Table	
14.5.1	Overall hematological response rate
Figures	
14.5.1	Overall hematological response rate at beginning of cycle 5
Listing	
16.5.1	Response assessment

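### PFS is censored at the last observation or follow-up visit, although progression counts only on a response assessment, so event-free patients off treatment or in Part 2c are carried as progression-free through unassessed time

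*SAP*

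**What the plan says.** **Event.** SAP 7.7.6 takes progression as "defined as first time having Progressive disease (PD) or Progression or relapse after HI on response assessment". Death is the other event.

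**Censoring.** Under the same section, a subject who has neither progressed "nor died will be censored on the date of the last observation". SAP 6.2.2 has the same rule, and neither place defines an observation. Protocol 2.3.2 says: "A subject who has neither progressed nor died will be censored on the date of last follow-up visit".

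**When progression can be seen.** SAP 8.3 gives the primary-phase times: "Response assessments of visit 5(W9 C3) and visit 9(W17 C5) will be listed". Responders are assessed again in the extension (Parts 2a and 2b). For non-responders who continue (Part 2c), the schedule footnote reads "Optional response assessment and lab measurements to be done according to standard of care". Part 3 (EOT and follow-up) has no row for response assessment, peripheral blasts or local marrow cytology. Marrow at EOT is listed under central assessments, and only when the previous procedure is more than 90 days old.

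**Last contact.** Patients who stop "will undergo an EOT visit at the latest 14 days after the decision of treatment discontinuation" (Protocol 5.1). FU2 follows about 2 months after EOT, and "FU2/EOS can be carried out on the phone and represents the last study visit for the patient".

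**The neighbouring endpoint.** For duration of response, SAP 7.7.7 states that the "subject will be censored on last documented response assessment".

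**The concern.** A patient should stay in the PFS risk set only while a progression, if it occurred, could be recorded. Here the risk set runs on to the last contact, while recording of progression ends with the last response assessment. Between the two, only death can count. A patient who progresses silently and is still alive at FU2 is entered as censored without progression.

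The usual path through the trial leads there. Non-responders at week 17 normally stop and go to follow-up, and the SAP document history reports no responders at the interim analysis. SAP 8.4.2 plans a median, a rate at a redacted week, and an estimate over all study data at hard lock, so the affected part of the curve will be reported. PFS and duration of response share the progression event but are censored by different rules, with no reason given.

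**Working it through.** The documents state no PFS assumption and no gap between assessment and censoring, so there is no planned figure to reproduce.

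**1. Length of the unassessed interval**

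Inputs: V9 on study day 113 (Protocol VII, Part 1); EOT 0 to 14 days after the decision and FU2 about 2 months after EOT (Protocol 5.1), taken as 2 × 30.44 = 60.9 days; FU2 window ±14 days (Protocol 8.1).

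Gap = (decision to EOT) + 60.9 + (window)

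- EOT on the decision day: 0 + 60.9 = 60.9 days = 8.7 weeks
- EOT at 14 days: 14 + 60.9 = 74.9 days = 10.7 weeks
- EOT at 14 days, FU2 at the late edge: 14 + 60.9 + 14 = 88.9 days = 12.7 weeks

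The shortest case, with FU2 at the early edge, is 60.9 − 14 = 46.9 days = 6.7 weeks. Time spent waiting for marrow results adds to each figure. The alternative wording in Protocol 7.7, 3 months after the last dose, gives about 13 weeks. If the last marrow is 90 days old at EOT and so is not repeated, the gap is 90 + 60.9 = 150.9 days = 21.6 weeks.

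A stable-disease non-responder is thus censored near day 113 + 14 + 61 = 188, although last assessed on day 113.

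**2. Direction**

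For patients not yet known to have progressed, the rule adds time at risk but lets only deaths be counted in it. Undetected progressions in that interval are lost. The estimate can only move up relative to true PFS, and deaths offset this only in part.

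**3. Size, under stated assumptions**

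Kaplan-Meier simulation. Assumed, not from the documents: exponential progression with median 10 or 13 weeks; median time to death 60 weeks before progression and 10 weeks after it; no responders; early discontinuation either none or exponential with mean 40 weeks. Assessments fall 8 and 16 weeks after day 1 (study weeks 9 and 17), and FU2 is 9.7 weeks after stopping. Ranges run from the 10-week to the 13-week median.

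| | True PFS | Present rule | Excess (points) |
|---|---|---|---|
| 16 weeks (study week 17), no early discontinuation | 27–35% | 27–35% | about 0 |
| 16 weeks, with early discontinuation | 28–36% | 34–41% | about 6 |
| 24 weeks, no early discontinuation | 14–21% | 23–30% | about 8–9 |
| 24 weeks, with early discontinuation | 14–21% | 27–34% | about 13 |

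The week-17 excess comes from patients who stop early and miss one or both assessments while staying at risk. The documents give no rate for this.

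A second simulation used progression medians of 90, 120 and 180 days, 15% early discontinuation, and 0 or 20% responders. The present rule was 2 to 3 points high at week 17 and 9 to 12 points high at day 187. The late bias is therefore not confined to fast progression.

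**4. What the alternative rule does**

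In the first simulation, censoring at the last response assessment and counting deaths within 8 weeks of it gives 27–35% at 16 weeks without early discontinuation and 26–33% with it, so within about 2 points of truth. At 24 weeks it gives 0%, against a true 14–21%: after the last assessment the only off-treatment patients left at risk are those about to die. The second simulation, counting every later death, gave 0 to 19% at day 187 against a true 16–34%. The alternative rule is sound up to the last scheduled assessment and unusable beyond it.

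**The case against.** Several counter-arguments have force.

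- **The median.** A reader might set a true median of about 9 to 11 weeks against 11 to 16 weeks under the present rule and blame the censoring. That does not hold. With 8-weekly assessment, complete follow-up and no censoring, the same model already gives 10.8 to 16.0 weeks. Without early discontinuation, the present rule gives the same values. Most of the contrast is detection delay, which no censoring rule removes.
- **How many patients.** A reader might infer that, with most patients non-responders, most of the PFS data end in unassessed time. Non-responders who progress on assessment or die have events. Only event-free patients are affected: 21–38% of patients were censored under the present rule in the simulation.
- **The reported timepoint.** The week for the planned PFS rate is redacted. If it is week 17, that rate may be little affected. The median and the hard-lock estimate would still use the whole curve.
- **Other sources of progression.** The PD definition includes peripheral blasts and new extramedullary disease, and follow-up records the state of condition. Under SAP 7.7.6, however, progression must be found on a response assessment, and Part 3 schedules none. Responders in the extension are also assessed on suspected progression, so the concern does not extend to them while they stay on that schedule.
- **Status of the endpoint.** PFS is secondary and the analysis exploratory. That limits the severity. It does not justify describing unassessed time as progression-free.

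**Conclusion.** The concern holds for event-free patients who are off treatment or in Part 2c. The present rule keeps them at risk for about 9 to 13 weeks after the V9 marrow in the usual case, and for as long as they are seen in Part 2c, with no scheduled means of recording progression. The direction is upward and follows from the documents. The size does not: about 8 to 13 points at 24 weeks and 0 to 6 points at week 17 rest on assumed progression medians of 10 to 13 weeks and on an assumed range of early discontinuation.

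The documents do not support a claim that the week-17 rate is necessarily distorted, or that simply switching to the duration-of-response rule yields an unbiased curve. That rule understates PFS once scheduled assessment has ended. This should be corrected before analysis, but it does not touch the primary endpoint.

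**What to change.** 1. In SAP 7.7.6, SAP 6.2.2 and Protocol 2.3.2, censor at the date of the last response assessment without progression. A patient who is alive with no post-baseline assessment is censored on day 1.
2. State a fixed window, in weeks after the last assessment, within which a death counts as an event. A death after the window leaves the patient censored at that assessment. Do not tie the window to the next scheduled assessment, because patients in Part 3 have none and those in Part 2c have only optional ones.
3. Do not report PFS rates or medians, or plot the Kaplan-Meier curve, beyond the last scheduled response assessment. That is week 17, except for patients in the Part 2a or 2b assessment schedule.
4. Keep the present rule as a labelled sensitivity analysis, with the last observation defined.
5. Reconcile the two follow-up statements (about 2 months after EOT; 3 months after the last dose), since they set the censoring date in that sensitivity analysis.

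The cost is wording in two SAP sections, one line in the protocol endpoint, and one extra table. PFS becomes somewhat shorter and is not estimable after week 17 for patients who are not assessed. The change should be made before the data review meeting, by which the SAP must be final.

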#### 7.7.7 Duration of response

Duration of response (DoR) will be measured from the time measurement criteria are met for CR, CRi, PR, MLFS or SD (whichever is first recorded, defined in section 11.2 Appendix 2 a)) until the first date at which recurrent or progressive disease is objectively documented for patients with confirmed CR, CRi, PR, MLFS or SD criteria met. Therefore:

DoR [days] = first date with PD response criteria after response – date of CR, CRi or PR response criteria +1

If there was no progressive disease documented, subject will be censored on last documented response assessment:

DoR [days] = date of last response assessment – date of CR, CRi or PR response criteria +1

#### 7.7.8 Best overall response

Best overall response will be defined as the best response recorded from the start of the treatment until diagnosis of disease progression. Response hierarchy considered as order of appearance on section 11.2 Appendix 2 a)

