2.3 Study endpoints

2.3.1 Primary endpoint

The primary endpoint of the study is defined as overall hematological response rate as assessed in [REDACTED] of treatment with imetelstat.

All patients with one of the following responses assessed by samples and procedures taken/carried out at [REDACTED] are defined as responders (assessed through the combined response criteria for MDS and AML used in this trial (see Appendix III a), section 16.3):

[1] CR, CRi, PR as defined in Appendix III a)

[2] Hematologic improvement (for one or several lines) as defined in Appendix III a)

Response rate is calculated as follows: number of responders divided by the number of all patients of the analysis set. Patients for whom the overall hematologic response cannot be determined will be considered as treatment failures.

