16.2 Appendix II: International Prognostic Scoring System Score Revised (IPSS-R)

According to: Greenberg PL, Tuechler H, Schanz J, et al. Revised international prognostic scoring system for myelodysplastic syndromes. Blood 2012;120(12):2454–65.

Points for calculation							
	0	0.5	1	1.5	2	3	4
% blasts in BM	≤ 2	-	> 2 - < 5	-	5 - 10	> 10	-
Karyotype	very good ¹	-	good ²	-	inter-mediate ³	poor ⁴	very poor ⁵
Hemoglobin (g/dl)	≥ 10	-	8 - < 10	< 8	-	-	-
Platelets (/nl)	≥ 100	50 - < 100	< 50	-	-	-	-
Neutrophils (/nl)	≥ 0.8	< 0.8	-	-	-	-	-

Risk Score	
Very low risk	≤ 1.5
Low risk	> 1.5 - 3
Intermediate risk	> 3 - 4.5
High risk	> 4.5 - 6
Very high risk	> 6

For IPSS-R classification you can also use the “MDS Center” App which is available in the Apple Store or Google Play Store.

16.3 Appendix III:

a) Combined response assessment criteria for MDS and AML

Based on IWG 2018 criteria (MDS)¹ and the criteria of the European LeukemiaNet (AML)²

CATEGORY	DEFINITION
Complete remission (CR)	Bone marrow blasts <5%; absence of circulating blasts and blasts with Auer rods; absence of extramedullary disease; ANC $\geq 1.0 \times 10^9/L$ (1000/ μL); platelet count $\geq 100 \times 10^9/L$ (100 000/ μL)
CR with incomplete hematologic recovery (CR _i)	All CR criteria except for residual neutropenia ($<1.0 \times 10^9/L$ [1000/ μL]) or thrombocytopenia ($<100 \times 10^9/L$ [100 000/ μL])
Partial remission (PR)	All hematologic criteria of CR; decrease of bone marrow blast percentage to $\geq 5\%$; and decrease of pretreatment bone marrow blast percentage by at least 50%
Morphologic leukemia-free state (MLFS)	Bone marrow blasts <5%; absence of blasts with Auer rods; absence of extramedullary disease; no hematologic recovery required
Stable disease (SD)	Absence of CR, CR _i , PR, MLFS; and criteria for PD not met

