#### **7.7.4 Hematological response**

All patients with one of the following responses assessed by samples and procedures taken/carried out at visit ■ in cycle ■ are defined as responders (assessed through the combined response criteria for MDS and AML used in this trial (see section 11.2 Appendix 2)):

- [1] CR, CRi, PR as defined in section 11.2 Appendix 2 a )
- [2] Hematologic improvement (for one or several lines) as defined in section 11.2 Appendix 2 a )

If any of those criteria is fulfilled, the subject will be classified as responder. Otherwise, he will be classified as non-responder. Patients for whom the overall hematologic response cannot be determined will be considered as treatment failures.

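### Best overall response hides patients who respond by hematologic improvement alone, and duration of response has three conflicting definitions, none of which includes it

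*SAP*

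**What the plan says.** **Primary endpoint.** Protocol 2.3.1 and SAP 7.7.4 give two routes to being a responder. One is remission ("1] CR, CRi, PR as defined in section 11.2 Appendix 2 a"). The other is HI ("2] Hematologic improvement (for one or several lines) as defined in section 11.2 Appendix 2 a"). Either is enough: "If any of those criteria is fulfilled, the subject will be classified as responder".

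**BOR.** SAP 7.7.8 takes the best response recorded up to progression and ranks the categories by where they stand in the criteria table: "Response hierarchy considered as order of appearance on section 11.2 Appendix 2 a". SAP 8.4.3 reports BOR in Table 14.6.4 as counts and percentages per category.

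**DoR.** SAP 7.7.7 says "Duration of response (DoR) will be measured from the time measurement criteria are met for CR, CRi, PR, MLFS or SD", whichever is recorded first. The event and censoring formulas in the same section subtract the date of CR, CRi or PR only. Protocol 2.3.2 has a third list: "measured from the time measurement criteria are met for CR, CRi, PR or SD". The SAP text ends the duration at recurrence or progression. The event formula ends it at PD only.

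**Related rules.** PFS in SAP 7.7.6 counts progression or relapse after HI as an event. Protocol 5.1.3 and 8.1.5 class every outcome other than CR, CRi, PR or HI as non-response, and say that MLFS is recorded but does not qualify a patient to continue.

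**The concern.** The primary response rate, BOR and DoR should describe the same responders, and as written they do not. A patient counted as a responder in Table 14.5.1 on HI alone would normally appear in Table 14.6.4 under SD, with nothing in that table to show the HI. Table 14.6.3 could be built on two different populations depending on whether the programmer follows the text or the formulas of SAP 7.7.7. If the text is followed, time in stable disease is pooled with time in remission, and patients whom the protocol calls non-responders contribute to the median. Losing HI ends PFS, yet gaining HI never starts DoR. The trial no longer has a confirmatory test (protocol 10.1), so its descriptive tables are what readers will use.

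**Working it through.** The plan states no figure for this point, so the check is of the definitions.

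**1. Where HI ranks.** The rows of SAP Appendix 2 a), which match protocol Appendix III a), run CR, CRi, PR, MLFS, SD, PD, hematologic relapse, then HI and its subtypes. Under SAP 7.7.8, HI is therefore below PD and relapse.

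**2. Whether HI can be the top category.** SD is residual: no CR, CRi, PR or MLFS, "and criteria for PD not met". HI is not among its exclusions. Take a patient with HI and let each of CR, CRi, PR, MLFS and PD be present or absent. That gives 2^5 = 32 combinations, some of them clinically impossible but all covered by the logic. Assign SD when none of the five is present, then pick the highest row:

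| Highest row | Combinations |
|---|---|
| CR | 16 |
| CRi | 8 |
| PR | 4 |
| MLFS | 2 |
| SD | 1 |
| PD | 1 |
| HI | 0 |

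The total is 16 + 8 + 4 + 2 + 1 + 1 = 32. A patient who is a primary responder on HI alone has no CR, CRi or PR, which leaves the last 2 + 1 + 1 = 4 non-zero combinations: MLFS, SD or PD. HI is never the top row as long as the marrow category can be assigned.

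**3. DoR definitions side by side.**

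| Source | Starts at | HI included | Ends at |
|---|---|---|---|
| Protocol 2.3.2 | CR, CRi, PR, SD | no | recurrence or progression |
| SAP 7.7.7 text | CR, CRi, PR, MLFS, SD | no | recurrence or progression |
| SAP 7.7.7 formulas | CR, CRi, PR | no | PD |

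An HI-only responder has no start date under the formulas. Under the text, the clock starts at the SD or MLFS that the patient also meets, not at the HI.

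**4. Size of the SD effect on one patient.** The protocol schedule (Part 1) puts visit 5 on day 57 and visit 9 on day 113. SAP 8.3 labels them weeks 9 and 17. For a patient with SD at visit 5, CR at visit 9 and an end date E:

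- text: E − 57 + 1
- formula: E − 113 + 1
- difference: 113 − 57 = 56 days

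With the ±3-day visit window the difference runs from 110 − 60 = 50 to 116 − 54 = 62 days, assuming no dose delays.

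**5. Who enters the DoR table.** A patient whose best outcome is SD enters under the SAP text and the protocol, but not under the formulas. The SAP document history (v1.1) records no responders in the interim data. If no cohort 1 patient responded later, the text fills that cohort's DoR table with SD and MLFS patients only, and the formulas leave it empty.

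**The case against.** The strongest reply is that nothing decisive depends on these tables. All analysis is exploratory, BOR and DoR are descriptive, and the primary rate comes from the eCRF responder item (SAP 6.2.1) and the SAP 7.7.4 rule, which includes HI. Visit 5 and visit 9 assessments are listed per patient, so an HI responder can be traced. This stands, and it limits the severity. It does not repair Tables 14.6.3 and 14.6.4.

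A second reply is that HI has its own heading in the appendix, so BOR may be meant as the marrow category with HI as a parallel dimension. That is a sensible reading, but SAP 7.7.8 does not state it, and no table pairs the two.

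A third is that the endpoint is named duration of best overall response and the protocol lists SD openly. Including SD is therefore the sponsor's stated definition and not a slip. That also stands. What remains are the SAP's addition of MLFS, the formulas that disagree with the text, and the fact that the first qualifying date is not the date of the best response.

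Some stronger inferences are tempting and not supported:

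- **HI can never appear.** BOR uses recorded responses and the eCRF layout is not shown. If the marrow category is not evaluable and only HI is recorded, HI could surface. The SAP has no rule for that case.
- **Responders will be shown as PD.** Marrow progression at the early assessment stops treatment (protocol 5.1.3 and 7.1), so a week-17 responder would ordinarily already have SD or better. PD as BOR would need a missing visit 5 or progression not acted on, together with PD and HI at visit 9.
- **The DoR median will rest mostly on non-responders.** The documents give no count of SD patients, so no such proportion can be stated.
- **Half of responders are affected.** HI is one of two routes in the definition, and its share of responders is unknown.

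**Conclusion.** The rules are wrong as written, at should-fix level, for two descriptive secondary endpoints. An HI-only primary responder with an evaluable marrow category is tabulated in Table 14.6.4 as SD, sometimes MLFS and rarely PD, so that table will not match Table 14.5.1. The mechanism that matters is the overlap of HI with SD. The position of HI below PD is a further sign that row order was not designed as a ranking.

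DoR cannot be programmed unambiguously: there are three start lists and two end events, and HI is in none of the lists. Following the text instead of the formulas lengthens DoR by 56 days on schedule for a patient with SD at visit 5 and CR at visit 9, and gives a duration to patients classed as non-responders.

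The conclusion rests on the printed row order, the printed SD definition and the schedule days. How many patients are affected depends on how many HI-only responders and SD patients there are, which the documents do not show. If the interim finding of no responders holds for all of cohort 1, the BOR mismatch concerns cohort 2 only.

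**What to change.** **SAP 7.7.8 and 8.4.3.** Replace the order-of-appearance rule with an explicit ranking of the marrow categories only: CR > CRi > PR > MLFS > SD > PD. Show HI (yes/no, by lineage) as a separate row or cross-tabulation beside BOR in Table 14.6.4, including patients whose marrow category is not evaluable. Every primary responder is then visible, and HI need not be ranked against MLFS, for which the documents give no basis.

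**SAP 7.7.7 and 6.2.2, protocol synopsis and 2.3.2.** Use one definition in text and formulas. Start DoR at the first date of CR, CRi, PR or HI at any assessment. Restricting it to visit 9 would drop remissions seen only before or after that visit. End it at PD, at hematologic relapse, or, for HI responders, at progression or relapse after HI, as PFS already does. Starting at HI without that end event would overstate HI durations. State which end event applies when HI is followed by a remission. If time in SD or MLFS is wanted, report it as a separate summary.

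**Cost.** SAP wording, derivation code, the protocol endpoint wording and fewer patients in the DoR table. The definition would change in an open-label trial after interim data, so record the reason in SAP section 9 and finalize before database lock.
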